Study Contact	M. [name]. Head of Clinical Affairs Miromatrix Medical Inc [name]	[contact] X-112 [contact] [contact]

Study Synopsis

Protocol Number	2016002
Title	Effectiveness of MIRODERM® Biologic Wound Matrix in the Treatment of Hard-to-Heal Diabetic Foot Ulcers
Short Title	MIRODERM H2H DFU
Sponsor	Miromatrix Medical Inc.
Name of Product	MIRODERM® Biological Wound Matrix Fenestrated MIRODERM® Biological Wound Matrix Fenestrated Plus
Device Description See IFU for complete details	MIRODERM Biological Wound Matrix MIRODERM is a non-crosslinked acellular wound matrix that is derived from porcine liver and is processed and stored in a phosphate buffered aqueous solution. MERODERM is available in a variety of sizes to be trimmed to meet the individual patient's needs and comes with or without fenestrations. MIRODERM is packaged in an inner sterile pouch and outer non-sterile pouch.
Intended Use See IFU for complete details	MIRODERM Biological Wound Matrix This device is intended for the management of wounds including: 
 • Partial and full thickness wounds • Pressure ulcers • Venous ulcers • Diabetic ulcers • Chronic vascular ulcers • Tunneled, undermined wounds • Drainage wounds • Surgical wounds (donor sites/grafts, post-Mohs' surgery, post-laser surgery, podiatric, wound dehiscence) • Trauma wounds (abrasions, lacerations, second-degree burns, and skin tears) 
The device is supplied sterile and is intended for one-time use

Background	Estimates are 8% of the United States population are diabetic and up to 25% of these will experience at least one diabetic foot ulcer in their lifetime. Treatment of diabetic foot ulcers can cost \$28,000 per episode. The presence of a diabetic foot ulcer increases chances of infection and future amputation. It is thus important to heal ulcers as expediently as possible. Ulcers refractory to treatment are of special concern and may prove responsive to treatment with MIRODERM Biologic Wound Matrix.
Study Center(s)	Up to 10 study centers will participate in this clinical trial.
Planned Sample Size	A minimum of 50 and not more than 65 subjects will be enrolled into this study.
Study Population	All patients who have at least one small to moderately sized diabetic foot ulcer and have been undergoing extended and unsuccessful treatment, as defined by failure of the wound to completely close over the previous 3 months and after application of at least 2 biological products.
Study Objectives	Primary Objective

	
The primary endpoint will be the proportion of subjects who achieve wound closure by or at 12-weeks post treatment with MIRODERM.
 
Secondary Objectives
 
Some secondary objectives of this study include documenting the time course of wound healing and assessing changes in quality of life. The safety profile will be further characterized by tracking related adverse events.


Study Design and Procedures
	
This is a multi-center post-market, single-arm, prospective follow-up study
 
Assessment and Roll-in Phase
 
Subjects will be recruited by the treating physicians, screened for eligibility, invited to participate in the study and provide informed consent. The subject's demographics, medical history, co-morbidities and wound characteristics will be documented and the subject will complete a SF-36 quality of life questionnaire. Subject will be instructed on proper nutrition.
 
Wound will undergo sharp debridement, be traced, photographed, and dressed per standard of care. Two tissue sections of at least 2mm will be retained for histological analysis. Subject will be fitted with and instructed on an offloading device. Subjects will return for MIRODERM treatment in two weeks.
 
Treatment Phase
 
On treatment day, wound will undergo sharp debridement, be traced, photographed and MIRODERM Biologic Wound Matrix will be applied. After treatment, subjects will be considered enrolled into the trial. Details of treatment will be documented.
 
Subject will present weekly for the next twelve weeks. The dressing will be changed and may undergo further MIRODERM treatment if indicated. The wound will be traced and photographed. Physician will document their assessment on whether the wound is 100% closed.
 
Subjects whose wound is completely closed at or prior to 12-weeks post-treatment, will be instructed to return 1-week following for a confirmation visit. Subjects whose wound is not assessed as closed by 12-weeks post-treatment, will have two tissue sections of at least 2mm collected, complete a quality of life assessment, and will then be discontinued per protocol.
 
Confirmation Phase
 
Subject will complete a quality of life assessment and have their wound area photographed. Physician will confirm the wound is still closed and the subject will be discontinued per protocol. If wound has reopened subject will return to the treatment phase.

Subject Participation
	
Subjects can be expected to reasonably participate in the study for a minimum of 9 weeks and a maximum of 15 weeks depending treatment course.


Inclusion Criteria
	
To be included in this study, subjects must:
 
 Be 18 years old or older at time of initial visit Have Type I or Type II diabetes Be willing and able to sign an informed consent Have a neuropathic diabetic foot ulcer with the following characteristics: 
 • Is greater than 1 cm² and less than or equal to 12 cm²

	
 • Has failed to close following at least 2 treatments with a biologic • Has been present for 90 days or longer • Does not show signs of infection • Is full thickness (Wagner Grade I or II) • Located distal to the malleolus • Depth of less than or equal to 5 mm • No exposed capsule, tendon or bone • No tunneling, undermining or sinus tracts • Not between the toes 
Be willing and able to maintain required off-loading of affected limb Be willing and able to perform necessary dressing changes Have at least one of the following:
 
 • An Ankle-brachial index (ABI) \geq 0.8 • TcPO₂ of \geq 30 mmHg • A toe pressure of \geq 50 mmHg

Exclusion Criteria
	
To be included in this study, subjects must not:
 
Be pregnant or be planning to become pregnant during the study Have had a Chopart’s Amputation (or higher) Have a history of bone cancer of the affected limb Be undergoing dialysis Have active osteomyelitis or be receiving treatment for osteomyelitis Be diagnosed with unstable Charcot Foot on the affected side Have an HbA1c level of \geq 12% within the past 90 days Have another ulcer within 2 cm of the study ulcer Be immunocompromised or at risk of immunosuppression as determined by the treating investigator Have a known collagen vascular disease or connective tissue disease Have received treatment of the study ulcer with a skin substitute product or topical growth factor within the past 4 weeks Be participating in another medical research study Have a sensitivity to porcine material


Schedule of Visits
	
 1 Assessment and Roll-in (2-weeks prior to procedure) 2 Index Procedure 3 1-Week post-procedure (\pm 2 days) 4 2-Week post-procedure (\pm 2 days) 5 3-Week post-procedure (\pm 2 days) 6 4-Week post-procedure (\pm 2 days) 7 5-Week post-procedure (\pm 2 days) 8 6-Week post-procedure (\pm 2 days) 9 7-Week post-procedure (\pm 2 days) 10 8-Week post-procedure (\pm 2 days) 11 9-Week post-procedure (\pm 2 days) 12 10-Week post-procedure (\pm 2 days) 13 11-Week post-procedure (\pm 2 days)

	
14 12-Week post-procedure (\pm 2 days)
 
15 Confirmation: 13-Week post-procedure (\pm 2 days)
 
All subjects will be offered a \$25 gift card for completing weekly follow-up during the treatment phase.

Study Duration	1 Year
Assessment Tools	
Ankle Brachial Index
 
HbA1c
 
Monofilament test for neuropathy
 
Photograph
 
E-Z Graph Wound Assessment System
 
Sf-36v2 Health Survey

Primary Endpoint	Proportion of subjects who have a closed wound at or before 12 weeks after the index procedure.
Primary Hypothesis	
As an observational study, there is no formal hypothesis test. The precision of the estimate of the proportion of subjects who successfully close will be determined.
 
Assumptions:
 
 • A minimum 50 subjects • A 95% Confidence Interval of the estimate • A 2-sided confidence interval • Using exact Clopper-Pearson estimation 
The Confidence Intervals (CI) at selected success rates are as follows:
 
 • @ 25%; CI = 25.4% Boundaries 13.8%-39.3% • @ 50%; CI = 28.9% Boundaries 35.5%-64.5% • @ 75%; CI = 25.4% Boundaries 60.7%-86.2% 
Thus, a sample size of 50 should allow for a reasonable estimate of treatment success at 12 weeks and for reasonable comparisons to historical controls.

Statistical Analysis	
Descriptive statistics including but not limited to mean, standard deviation, frequency and percentages will be used to describe demographics, medical history, and characterize baseline variable as appropriate.
 
A Z-test will be used to assess whether the proportion of subjects that were successful is greater than zero. Kaplan-Meier analysis will be used describe the survival curve assuming complete closure as the event of interest. A repeated measure ANOVA will be used to assess changes in, wound area and quality of life over time.

TABLE OF CONTENTS

1	Background	13

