4.2 Primary Endpoint

The primary endpoint will be the proportion of subjects who achieve wound closure by or at 12-weeks post treatment with MIRODERM.

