4.3 Secondary Objectives

Some secondary objectives include but are not limited to:

- Describe the time course to full wound closure
- Determine the subjects' quality of life score before and after treatment
- Characterize the safety profile of MIRODERM and the procedure
- Explore the histological characteristics of those who successfully heal and those who don't

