If wound has not closed, the dressing will be changed (subsequent to any needed treatment as described in the above paragraph) and the subject will return the following week. If the wound is healed subject will return for a confirmation visit one week later. If, after 12 weeks, the wound is not healed, subject will complete a SF-36 quality of life survey, two tissue sections of at least 2mm from the wound area will be collected and the subject will be discontinued from the study per protocol.

Confirmation Phase

Subject will complete a quality of life assessment and have their wound area photographed. Physician will confirm the wound is still closed and the subject will be discontinued per protocol. If wound has reopened subject will return to the treatment phase.

Subjects whose wound has been assessed closed will return for a confirmation visit. The wound will be assessed for closure. If the wound is still closed, the wound area will be photographed, the subject will complete a SF-36 quality of life survey and be discontinued from the study per protocol. If wound has reopened, subject will return to the follow-up phase at the appropriate post-treatment week continuing there until wound closure or through 12 weeks of follow-up as described in “Treatment Phase” above.

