6.7.4 Follow-up Stipend

Subjects will receive a \$25 gift card at each follow-up. Distribution of gift card will be documented.

The following activities will be completed by subjects who present at the 12-week post-treatment visit and have a wound that is not fully closed.

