6.8 Confirmation Visit (1 week after complete closure or Visit 15; Week 16)

6.8.1 Wound Closure Assessment

Wound will be assessed for closure. If wound is still closed subject will continue to 6.8.2 below. ***If it is determined that the wound is reopened,*** subject will have wound assessed (6.7.2) and treated as needed (6.7.3). Subject will continue in the follow-up phase (6.7) until wound is closed or 12 weeks of follow-up have been completed.

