6.10.4 Wound Assessment and Treatment CRF

This will document whether the wound is closed. To be closed there must be 100% epithelialization of the wound, no discernable exudate, and no further need for dressing.

Wound area and volume will be assessed by gross measurement of length, width and depth and assessed for infection.

With initial application during the treatment visit, and then when clinically indicated additional applications of MIROMESH will be documented including lot number, type, and size of MIRODERM Biologic Wound Matrix.

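### As worded, the primary endpoint counts any first closure by the 12-week visit, and nothing visible ties it to the protocol's own one-week confirmation

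*Combined protocol and SAP*

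**What the plan says.** The endpoint is stated twice, each time without a confirmation condition. The Synopsis has "Proportion of subjects who have a closed wound at or before 12 weeks after the index procedure"; section 4.2 has "The primary endpoint will be the proportion of subjects who achieve wound closure by or at 12-weeks post treatment with MIRODERM". The primary objective in section 4.1 is silent on confirmation too.

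Section 6.10.4 defines closure from a single examination: "To be closed there must be 100% epithelialization of the wound, no discernable exudate, and no further need for dressing".

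The protocol then schedules a second look. In the Synopsis: "Subjects whose wound is completely closed at or prior to 12-weeks post-treatment, will be instructed to return 1-week following for a confirmation visit". Table 1 lists a closure assessment at that visit. The result is used for two things:

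- **Patient flow.** Section 6.1: "If wound has reopened, subject will return to the follow-up phase at the appropriate post-treatment week". Section 6.8.1: "Subject will continue in the follow-up phase (6.7) until wound is closed or 12 weeks of follow-up have been completed". The Synopsis also sends a reopened wound back to treatment, but sets no time limit.
- **Study exit.** Section 6.9 has one exit for a wound that closed and held at confirmation, and another for a wound still unhealed after 12 weeks of follow-up.

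Section 14.2 lists recurrence of the wound among reportable adverse events. The Synopsis makes complete closure the Kaplan-Meier event, without saying whether first or confirmed closure is meant. Section 7 mentions neither confirmation nor reopening, and says that missing data are ignored.

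**The concern.** The endpoint and the closure definition together give a workable rule: a subject succeeds at the first visit, up to 12 weeks, at which the wound is judged closed. What happens a week later does not enter. The rest of the protocol treats a reopened wound as not yet healed, so one subject can be a primary success and also leave the study as unhealed.

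This is the only primary result of a single-arm study, and the plan means to set it beside historical controls (Synopsis) and the literature (section 7). With no concurrent arm, the definition of success directly sets the figure being compared. The documents do not say whether the comparators used first or confirmed closure. There is no formal hypothesis on this endpoint's size, so no pass/fail decision is at stake; the reported estimate is.

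**Working it through.** **1. The plan's own intervals.** Inputs from section 7: n = 50, two-sided 95%, exact Clopper-Pearson. Lower limit = Beta quantile (0.025; x, n-x+1); upper limit = Beta quantile (0.975; x+1, n-x).

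| Rate | x | Recomputed | Plan |
|---|---|---|---|
| 25% | 12.5 | 13.84-39.26 | 13.8-39.3 |
| 50% | 25 | 35.53-64.47 | 35.5-64.5 |
| 75% | 37.5 | 60.74-86.16 | 60.7-86.2 |

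The figures reproduce (the outer rows need a non-integer count, which the formula accepts). They are not in dispute.

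**2. How the text scores typical courses.** The weeks are post-procedure and illustrative.

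| Course | Endpoint as worded | Rest of protocol | Confirmed-closure rule |
|---|---|---|---|
| Closed at 6, closed at 7 | Success | Exits as closed | Success |
| Closed at 6, open at 7, closed at 10 and 11 | Success | Exits as closed | Success, dated at 10 |
| Closed at 6, open at 7, open at 12 | Success | Exits as unhealed (6.9) | Not a success |
| First closed at 12, open at 13 | Success | Synopsis: back to treatment; 6.8.1: follow-up limited to 12 weeks | Not a success |
| Closed at 6, never seen again | Success | Exits as lost to follow-up; no scoring rule | Not confirmed |

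For the third course, section 6.7 applies the 12-week activities reserved for open wounds: "The following activities will be completed by subjects who present at the 12-week post-treatment visit and have a wound that is not fully closed".

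**3. Direction and size.** Let N be all treated subjects, C those with any closure by the 12-week visit, and U those among C who never reach a confirmed closure.

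- Literal rate = C/N; confirmed rate = (C - U)/N.
- Difference = U/N, which cannot be negative, because every confirmed closure is also a first or later closure by 12 weeks.
- One such subject: 1/50 = 2.0 points; 1/65 = 1.5 points.
- Five such subjects: 5/50 = 10.0 points; 5/65 = 7.7 points.

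**4. Illustration at n = 50 with C = 25.** The values of U are assumptions; the documents give no reopening rate.

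| U | Confirmed rate | Exact 95% CI |
|---|---|---|
| 0 | 25/50 = 50.0% | 35.5-64.5 |
| 1 | 24/50 = 48.0% | 33.7-62.6 |
| 2 | 23/50 = 46.0% | 31.8-60.7 |
| 5 | 20/50 = 40.0% | 26.4-54.8 |

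**The case against.** The best defence is that confirmed closure was meant all along. Section 6.9 lets a closed wound leave the study as closed only if it holds at confirmation, and sections 6.1 and 6.8.1 keep a reopened wound in follow-up. Closure is recorded at every visit from treatment through confirmation, so both rates can be computed from planned data. The subject flow chart (6.4) and the sample forms (Appendix B) are not in the text available here and might show the link. And since the comparators' definitions are unknown, which rate should be primary is partly a matter of choice.

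Much of this stands. The intent is plausible, and the data will exist. But an exit rule does not score an endpoint. If confirmation was meant, the endpoint wording omits it; if first closure was meant, the plan should say so. Section 7 also allows analyses at any time as needed, which is a reason to settle the definition before results are seen.

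Some stronger readings are tempting but not supported:

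- *That the sponsor will count reopened wounds as successes.* The documents show an unstated link, not that intention.
- *That the final tissue sample shows the plan placing these subjects on the unhealed side of a histology comparison.* Section 4.3 does aim to "Explore the histological characteristics of those who successfully heal and those who" do not, but Table 1 and section 6.10.15 take the final sample only from unhealed subjects, section 6.7.6 allows it to be omitted, and no section assigns it to that comparison.
- *That the gap equals the share of wounds found open at confirmation.* It would only if none re-closed and was confirmed, and sections 6.1 and 6.8.1 allow for that.
- *That a wound open at Week 13 certainly gets no further follow-up.* The Synopsis and section 6.8.1 differ on this.

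**Conclusion.** The point holds as a gap in the endpoint definition. Read literally, the endpoint counts any closure by the 12-week visit, and no visible section makes success or the Kaplan-Meier event depend on confirmation. With all treated subjects as denominator, the literal rate is never below the confirmed rate, and exceeds it by 2.0 points at n=50 (1.5 at n=65) for each closure never confirmed.

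The total cannot be derived from the documents. It may be zero, and wounds that re-close and are confirmed reduce it. The 10-point example rests on an assumed five unconfirmed closures among 25. The point is worth fixing because the estimate is the study's sole primary result; it does not undermine the design.

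**What to change.** - **Endpoint.** Define primary success as closure under section 6.10.4 at a visit up to and including the 12-week visit, with the wound still closed at the confirmation visit one week later. A reopened wound counts only if it re-closes by the 12-week visit and that closure is confirmed.
- **Denominator.** Use all treated subjects and count a missed confirmation as not confirmed, as a stated exception to the missing-data rule in section 7.
- **Kaplan-Meier.** Date the event at the first visit of the confirmed closure. Do not count an unconfirmed closure as an event. Censor other subjects at their last closure assessment up to 12 weeks.
- **Sensitivity analysis.** Report first-observed closure alongside as the upper bound.
- **Reconcile.** The Synopsis and section 6.8.1 should agree on what happens to a wound first closed at Week 12 and found open at Week 13.

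The cost is a few sentences and one extra analysis; the confirmation assessment is already scheduled. The reported rate may be lower, and it is understated if wounds with a missed confirmation in fact stayed closed.

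A separate minor item: Table 1 places treatment at Week 3, final follow-up at Week 14 (14 - 3 = 11 weeks later) and confirmation at Week 15 (15 - 3 = 12). The Synopsis visit schedule and sections 6.7 and 6.8 give 12 and 13 weeks post-procedure, that is, study Weeks 15 and 16. These should be brought into line.

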4 OBJECTIVES OF THE CLINICAL INVESTIGATION

4.1 Primary Objective

The primary objective is to document the effectiveness of MIRODERM Biologic Wound Matrix, to close hard-to-heal DFUs at or within 12 weeks of initial treatment.

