7 STATISTICAL CONSIDERATIONS

As a prospective clinical outcome and survivorship study, there are no specific hypotheses to be tested. Data analysis may be conducted intermittently as needed or as requested by investigators without a power penalty and consist primarily of summary statistics and inferential statistics for changes in dependent measures over time.

Specific data analyses may include but are not limited to:

- **Demographics** and other pre-treatment characteristics will be summarized and characterized with appropriate descriptive statistics including error measures. Statistics may include mean, mode, median, range, inter-quartile range, minimum, maximum, frequency, cumulative frequency percentage and cumulative percentage. Results may be presented in a narrative and graphically.
- **Subject reported and dependent outcome measures** will be summarized and thoroughly characterized with the appropriate descriptive statistics including error measures. Statistics may include mean, mode, median, range, inter-quartile range, minimum, maximum, frequency, cumulative frequency percentage and cumulative percentage. Results may be presented in a narrative and graphically. Measures collected at multiple timepoints will also be analyzed using inferential statistics to assess changes over time, of special interest post-treatment changes from pre-treatment values. As appropriate a repeated measure ANOVA or Wilcoxon signed rank

test will be completed for each outcome measure. If a significant trend is identified, significance among time points may be further explored using the appropriate pair-wise comparisons. In all cases a p-value equal to or less than 0.05 will be considered significant. No corrections for multiple pair-wise comparisons will be made.

Missing data will be ignored in statistical calculations while using the appropriate n (sample size) for any given statistic or test.

Sample Size Justification: The precision of the estimate of the proportion of subjects who successfully close will be determined.

Assumptions:

- A minimum 50 subjects
- A 95% Confidence Interval of the estimate
- A 2-sided confidence interval
- Using exact Clopper-Pearson estimation

The Confidence Intervals (CI) at selected success rates are as follows:

- @ 25%; CI = 25.4% Boundaries 13.8%-39.3%
- @ 50%; CI = 28.9% Boundaries 35.5%-64.5%
- @ 75%; CI = 25.4% Boundaries 60.7%-86.2%

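### The synopsis disclaims any formal hypothesis test, then plans a Z-test of the 12-week closure proportion against zero, a null at which the standard Z is undefined and which a single closure refutes.

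*Combined protocol and SAP*

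**What the plan says.** The synopsis defines the primary endpoint as "Proportion of subjects who have a closed wound at or before 12 weeks after the index procedure". Its Primary Hypothesis row states "As an observational study, there is no formal hypothesis test" and continues "The precision of the estimate of the proportion of subjects who successfully close will be determined". The assumptions listed there are at least 50 subjects and a two-sided 95% interval, "Using exact Clopper-Pearson estimation". The Statistical Analysis row then says: "A Z-test will be used to assess whether the proportion of subjects that were successful is greater than zero". It gives no variance form, sidedness or significance level for that test.

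Section 7 says "there are no specific hypotheses to be tested" and describes the analyses as mainly summary statistics and "inferential statistics for changes in dependent measures over time". It repeats the precision statement and the interval assumptions but does not name the Z-test. Its 0.05 threshold appears in the bullet on outcome measures, which deals with changes over time. Section 4.1 gives the primary objective as to "document the effectiveness of MIRODERM Biologic Wound Matrix" in closing hard-to-heal ulcers within 12 weeks.

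**The concern.** There are two problems. The first is consistency: adjacent synopsis rows appear to rule out a test and then prescribe one on the primary endpoint, and Section 7 does not resolve the matter. The second is technical and does not depend on how the disclaimer is read. A proportion of exactly zero lies on the boundary of the parameter space. The usual Z-statistic does not exist there, and the hypothesis is disproved by a single event.

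What is at stake is interpretation. A study meant to document effectiveness could report a very small p-value on its primary endpoint when all that has been shown is that some wounds closed. A reader could take that p-value as evidence of a device effect.

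**Working it through.** **Inputs.** From the synopsis: null proportion 0, n = 50 (the minimum), maximum enrolment 65, exact two-sided 95% Clopper-Pearson interval. Assumed, because the plan is silent for this test: a 0.05 level, with one-sided and two-sided results both shown.

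**1. The plan's own intervals.** Using beta quantiles with x = 50p (12.5, 25 and 37.5), the limits are 13.84%–39.26%, 35.53%–64.47% and 60.74%–86.16%. These agree with the tabulated values to rounding. The 25% and 75% rows are not attainable counts out of 50, so neighbouring counts are used below.

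**2. Z with the null variance (the standard form).** Z = (p̂ − p0)/√(p0(1 − p0)/n). With p0 = 0 the denominator is √(0 × 1/50) = 0. Z is undefined at n = 50 and at every other n.

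**3. The hypothesis itself.** If the true proportion is 0, P(X ≥ 1) = 0, so one closure refutes it. If the true rate were only 5%, the chance of at least one closure would be 1 − 0.95^50 = 92.3% (96.4% with n = 65).

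**4. Z with the sample variance.** Z = p̂/√(p̂(1 − p̂)/n). For 3 of 50: 0.06/√(0.06 × 0.94/50) = 1.79. For n = 50:

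| Closures | Rate | Z | One-sided p | Two-sided p | Exact 95% interval |
|---|---|---|---|---|---|
| 0 | 0% | undefined | – | – | 0%–7.1% |
| 1 | 2% | 1.01 | 0.156 | 0.312 | 0.05%–10.65% |
| 2 | 4% | 1.44 | 0.074 | 0.149 | 0.5%–13.7% |
| 3 | 6% | 1.79 | 0.037 | 0.074 | 1.3%–16.5% |
| 4 | 8% | 2.09 | 0.019 | 0.037 | 2.2%–19.2% |
| 12 | 24% | 3.97 | <0.0001 | <0.0001 | 13.1%–38.2% |
| 13 | 26% | 4.19 | <0.0001 | <0.0001 | 14.6%–40.3% |
| 25 | 50% | 7.07 | <0.0001 | <0.0001 | 35.5%–64.5% |
| 37 | 74% | 11.93 | <0.0001 | <0.0001 | 59.7%–85.4% |
| 38 | 76% | 12.58 | <0.0001 | <0.0001 | 61.8%–86.9% |

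Rejection starts at 3 closures one-sided and 4 two-sided. At n = 65 the counts are the same: 3 (4.6%; Z = 1.77, one-sided p = 0.038) and 4 (6.2%; Z = 2.06, two-sided p = 0.039).

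**5. Test against interval.** The exact lower limit is above zero for every count of 1 or more. The sample-variance test can therefore disagree with it about zero only at 1–2 closures of 50 (one-sided) or 1–3 (two-sided). At a true rate of 25%, the lowest the plan tabulates, P(1 ≤ X ≤ 2) = 0.000087 and P(1 ≤ X ≤ 3) = 0.000498, that is, 0.009% and 0.05%. At such rates the test adds nothing to the interval.

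**The case against.** The wording conflict can be read away. The same synopsis row plans a repeated-measures ANOVA, and Section 7 sets a 0.05 threshold for changes over time, so the authors probably mean that no confirmatory hypothesis drives the study. Section 7's list of analyses is also expressly open-ended, so its silence on the Z-test is not a contradiction. Both points stand. On that reading the inconsistency is one of wording.

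Zero may also have been chosen deliberately. Eligible ulcers have been present for at least 90 days and have failed at least two biologic treatments, and Section 7 closes by anticipating comparison with a history of not healing. That explains the choice but does not justify it, because past non-closure does not make the expected future rate zero. Section 6.6.1 itself provides for a wound found closed at the Treatment Visit, before any MIRODERM is applied. Subjects also receive debridement, off-loading and nutrition instruction at roll-in. A closure rate above zero is therefore not evidence of a device effect.

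It is also true that one closure does not settle a sample-variance Z-test, where 1 of 50 gives p = 0.156 one-sided. That counts further against the test, since it fails to reject a null that the data have already ruled out.

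Finally, a test against a justified non-zero benchmark would be another repair. The synopsis and Section 7 mention historical controls and the literature but give no numerical value, so no such test can be built from the documents.

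**Conclusion.** The concern holds and is minor. The planned test is undefined in its standard form. In its sample-variance form it rejects from 6%–8% closure at n = 50, or 4.6%–6.2% at n = 65, far below any rate in the plan's own precision table. Those thresholds assume a 0.05 level and the sample variance, neither of which is stated for this test; the ranges run from one-sided to two-sided. That the standard form is undefined, and that a single closure refutes the null, need no such assumption.

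Nothing else depends on the test. The sample size rests on interval precision, which reproduces, and the closure estimate and Kaplan-Meier analysis are unaffected. The harm is limited to inconsistent wording and a p-value that could be mistaken for evidence of effectiveness.

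One inference should be noted. The documents give the Clopper-Pearson interval only among the sample-size assumptions. Treating it as the intended primary analysis relies on the statement that precision will be determined.

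**What to change.** Delete the Z-test sentence from the synopsis. In both the synopsis and Section 7, state the primary analysis outright, for example:

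> The primary analysis is the proportion of subjects with wound closure at or before 12 weeks after the index procedure, with its exact two-sided 95% Clopper-Pearson interval; no hypothesis test is performed on the primary endpoint.

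This aligns the two places and makes explicit an analysis that now has to be inferred. The cost is a wording change only, with no new data and no change to the sample size. The sponsor gives up an uninformative p-value.
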